### **1.6.2. Abnormal Liver Function Tests**

Elevations of AST and/or ALT have been seen in subjects receiving ALN-TTRSC in completed and ongoing clinical studies. The majority of abnormalities have been mild and transient elevations of ALT and/or AST  $<3\times\text{ULN}$ , and are not associated with changes in total bilirubin or clinical symptoms. In some subjects, higher ALT and/or AST elevations have been observed and led to interruption or discontinuation of study treatment. Serious hepatic adverse events have also been reported, including a case of possible drug-induced hepatitis and cholestasis; in this case a contributory role of study drug could not be excluded.

The risk of liver toxicity is lowered by requiring patients to have adequate liver function at study entry, as well as regular monitoring of LFTs during the study. If a patient develops clinical signs or symptoms such as unexplained anorexia, fatigue, jaundice, or dark urine, the Investigator should consider liver injury as a potential etiology.

Dose reduction may be considered in some cases after consultation with the Medical Monitor (see Section 5.6).

### **1.6.3. Vitamin A Lowering**

The suppression of serum levels of TTR and RBP is expected to result in the lowering of circulating vitamin A levels. Preclinical and clinical data have shown that the lowering of circulating vitamin A associated with suppression of RBP does not result in severe vitamin A deficiency. Furthermore, there are individuals with RBP/TTR mutations who have life-long low levels of circulating vitamin A and are essentially in good health, suggesting that there are compensatory transport mechanisms for vitamin A that are yet undescribed. This has also been confirmed in TTR knockout mice, which do not exhibit any manifestations of vitamin A deficiency, with vitamin A uptake by most tissues continuing in the absence of RBP. Provided there is adequate vitamin A in the diet, tissue stores of vitamin A should not be affected by the lowering of TTR and RBP. However, as the vitamin A content of the diet may vary between different countries and different individuals within a country, all patients on the study will be asked to take a supplement containing the recommended daily allowance of vitamin A of 2500-3000 IU.

## **1.7. Urgent Safety Measures**

In accordance with UK Law (Medicines for Human Use [Clinical Trials] as amended: Statutory Instrument 1031 Part 4 Section 30) the Sponsor and Investigator may take appropriate urgent safety measures in order to protect the subjects of a clinical trial against any immediate hazard to their health or safety. If such measures are taken, the Sponsor shall immediately (no later than 3 days from the date the measures are taken) give written notice to the licensing authority and the relevant Independent Ethics Committee (IEC) of the measures taken and the circumstances giving rise to those measures.

## **2. STUDY OBJECTIVES**

### **2.1. Primary Objective**

The primary objective of the study is to evaluate the safety and tolerability of long-term dosing with ALN-TTRSC.

### **2.2. Secondary Objectives**

Secondary objectives of this study are to assess the PD effect of long-term dosing of ALN-TTRSC on serum levels of TTR and the clinical effects of long-term dosing of ALN-TTRSC, including effect on mortality, hospitalization, and 6-MWT.

### **2.3. Tertiary Objectives**

Tertiary objectives of the study are:

- To further characterize the PK of ALN-TTRSC.
- To assess the clinical effects of long-term dosing of ALN-TTRSC including: echocardiogram, cardiac biomarkers (NT-proBNP and troponin T and I), quantitation of amyloid in fat pad aspirates, CMR, Kansas City Cardiomyopathy Questionnaire (KCCQ), 99m-Technetium (99mTc) imaging, estimated glomerular filtration rate (eGFR), New York Heart Association (NYHA) class, blood pressure, modified body mass index (mBMI), new onset or recurrence of atrial fibrillation, pacemaker placement, change in diuretic regimen, and EQ-5D Quality of Life (EQ-5D-QoL) questionnaire.
- To understand disease burden and healthcare utilization.

### 3. STUDY PLAN

#### 3.1. Overall Design

Protocol ALN-TTRSC-003 is an open-label, extension study designed to evaluate the long-term safety, clinical activity, and PK of subcutaneously administered ALN-TTRSC in patients with TTR cardiac amyloidosis who previously completed the ALN-TTRSC-002 study.

[figure not shown]
The study will be conducted either at newly added study sites or at the same study sites where patients completed participation in Study ALN-TTRSC-002.

Eligible, consenting patients will receive 5 daily doses of ALN-TTRSC (Day 0, 1, 2, 3, and 4) and a dose at Day 7. They will then receive once weekly doses for the duration of the study through Day 1337 (or ET). Doses will be administered at the clinic during Days 0 through 7. Dosing after Day 7 may be administered at home by a healthcare professional trained in the protocol, or at the clinic if dosing coincides with the clinic visit for other assessments. At the discretion of the Investigator, after the Day 84 dosing visit, and if the patient has not experienced any severe adverse events or SAEs considered related to the study drug within the previous 12 weeks, patients/caregivers may be trained by the Investigator or qualified site staff in the administration of the study drug, according to the protocol dosing requirements.

Patients must be screened prior to administration of study medication under this protocol. Screening/Baseline assessments may be performed during several clinic visits. Patients must have completed the ALN-TTRSC-002 study to be eligible for this study. If the final (Day 90) visit in the ALN-TTRSC-002 study is within 28 days of the first dose administered in this study, then visit procedures performed as part of the Day 90 visit do not need to be repeated at the Screening/Baseline visit. If the final (Day 90) visit in the ALN-TTRSC-002 study occurred within 90 days of the first dose administered in this study, the echocardiogram and CMR do not need to be repeated at the Screening/Baseline visit. Assessments not conducted as part of the ALN-TTRSC-002 Day 90 visit must be completed at the Screening/Baseline visit.

Clinic visits will be performed for Screening/Baseline, dose initiation during Days 0 through 7, and then approximately every 12 weeks through the End of Study visit (or ET), and at approximately 28 days following the End of Study visit (or ET) for a Follow-up visit.

A schematic of the protocol design is presented in [Figure 1](#).

**Figure 1: Study Schematic**

### 3.2. Safety Assessments

Safety evaluations will be performed as part of Screening/Baseline and approximately every 12 weeks during the treatment period (with the exception of eye examinations, which will be performed once a year). Some safety evaluations such as vital sign measurement and clinical laboratory tests will be performed more frequently.

Safety monitoring will include assessment of AEs, clinical laboratory tests (hematology, serum chemistry, thyroid function, coagulation, and urinalysis), 12-lead ECGs, vital signs (blood pressure, pulse rate, oral body temperature, and respiratory rate), eye examinations, and physical examinations.

### 3.3. Pharmacodynamic Assessments

Pharmacodynamic evaluation will include serial measurement of serum levels of TTR at specified time points. Serum levels of vitamin A will also be evaluated as a secondary PD biomarker.

### **3.4. Pharmacokinetic Assessments**

Samples for assessment of plasma concentration of ALN-TTRSC and possible metabolite analysis will be collected at various time points.

### **3.5. Exploratory Clinical Efficacy Assessments**

Clinical efficacy will be explored through mortality, hospitalization, and 6-MWT. Additional clinical assessments will be performed including echocardiogram, CMR, 99mTc imaging, circulating cardiac biomarkers (including NT-proBNP, troponins I and T), amyloid quantitation in fat pad aspirates, eGFR, mBMI, KCCQ, new onset or recurrence of atrial fibrillation, pacemaker placement, change in diuretic medication regimen, blood pressure, NYHA classification, and patient-reported QoL assessed by EQ-5D. Evaluations of clinical efficacy will be performed as part of Screening and approximately every 24 through 48 weeks during the treatment period.

### **Other Assessments**

Blood samples will also be collected to evaluate exploratory biomarkers (mutant: WT TTR levels and additional cardiac and hepatic-derived proteins that may include galectin-3 and ST2) and serology (anti-drug antibody [ADAs]).

Aliquots of serum samples will be taken and frozen, to permit testing of the effect of ALN-TTRSC on the expression of these exploratory biomarkers and serology.

Disease burden and healthcare utilization will be assessed approximately every 48 weeks using a patient reported pharmacoeconomics questionnaire.

## 4. PATIENT POPULATION

### 4.1. Eligibility of Patients

Approximately 25 patients who completed participation in Study ALN-TTRSC-002 are expected to be enrolled in this extension study.

### 4.2. Inclusion Criteria

Each patient must meet all of the following inclusion criteria during the Screening/Baseline period to be eligible for enrollment in this study:

1. Previously received and tolerated ALN-TTRSC in Study ALN-TTRSC-002; and completed Study ALN-TTRSC-002 through the Day 90 visit;
2. Adequate liver function, demonstrated by an AST and ALT  $\leq 2.5 \times$  ULN, total bilirubin  $< 2$  g/dL (34.2  $\mu$ mol/L), and albumin  $> 3$  g/dL ( $> 4.35$   $\mu$ mol/L);
3. Women of child-bearing potential (WOCBP) must have a negative pregnancy test, cannot be breast feeding, and must be willing to use a highly effective method of contraception (see Section 7.9.1) prior to Screening/Baseline, throughout study participation, and for 1 month after last dose administration;
  4. Males who agree to use appropriate means of contraception (see Section 7.9.2) throughout study participation until 1 month after last dose administration;
5. Patient, or patient's legal representative, is able and willing to provide written informed consent and the patient is willing to comply with the study requirements.

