	

2. Adequate liver function, demonstrated by an aspartate transaminase and alanine transaminase <math>\leq 2.5 \times</math> the upper limit of normal, total bilirubin <math>< 2 \text{ g/dL}</math> (34.2 <math>\mu\text{mol/L}</math>), and albumin <math>> 3 \text{ g/dL}</math> (<math>> 4.35 \mu\text{mol/L}</math>);

3. Women of child-bearing potential (WOCBP) must have a negative pregnancy test, cannot be breast feeding, and must be willing to use a highly effective method of contraception prior to Screening/Baseline, throughout study participation, and for 1 month after last dose administration;

4. Males who agree to use appropriate means of contraception throughout study participation until 1 month after last dose administration;

5. Patient, or patient's legal representative, is able and willing to provide written informed consent and the patient is willing to comply with the study requirements.

 
Each patient must not meet any of the following exclusion criteria to be eligible for enrollment in the study:
 

1. Estimated Glomerular Filtration Rate <math>< 20 \text{ mL/min}/1.73\text{m}^2</math> (using the Modification of Diet in Renal Disease [MDRD] formula);

2. Uncontrolled hypertension;

3. Uncontrolled ischemic heart disease;

4. Uncontrolled clinically significant cardiac arrhythmia;

5. Untreated hypo- or hyperthyroidism;

6. Prior major organ transplant;

7. Known or suspected systemic bacterial, viral, parasitic, or fungal infection;

8. Seropositive for hepatitis B virus, hepatitis C virus (HCV) or known to be human immunodeficiency virus positive;

9. Received an investigational agent other than tafamidis, diflunisal, doxycycline, or taouroursodeoxycholic acid, or an investigational device within 30 days prior to first dose of study drug;

10. Discontinued ALN-TTRSC-002 study due to a treatment-related AE;

11. Metastatic cancer within the past 5 years;

12. Any conditions which, in the opinion of the Investigator, would make the patient unsuitable for enrollment or could interfere with the patient's participation in, or completion of, the study.

--	---

	13. History of allergic reaction to an oligonucleotide or GalNAc.

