As of 05 January 2016, 25 patients have been treated with ALN TTRSC for approximately 8 months (range 1-13 months). Multiple doses of ALN TTRSC have been generally well-tolerated. The majority of AEs were mild or moderate in severity. The most common AEs related to study drug have been ISRs, usually characterized by transient erythema, pruritus, pain, or swelling at or around the injection site. Occasionally, these reactions have been recurrent, of longer duration and increased intensity. In some cases, ISRs have led to interruption or discontinuation of study drug. Elevations of ALT and AST have been observed, the majority of which have been mild, transient,  $<3\times$ ULN and not associated with any changes in total bilirubin or clinical symptoms. In several subjects, the elevations may have led to interruption and/or dose reduction of study treatment. There were no serious hepatic AEs.

ALN-TTRSC-004 is an ongoing, Phase 3 randomized, double-blind, placebo-controlled study of ALN-TTRSC in patients with FAC. Patients receive ALN-TTRSC 500 mg or placebo administered as 5 daily SC doses, followed by weekly SC doses for 18 months. As of 14 January 2016, 83 patients have been treated with blinded study drug for approximately 3 months (range 0-13 months). The majority of AEs were mild or moderate in severity. The most common AEs considered related to blinded study treatment have been ISRs. One patient developed symptoms of anorexia, weight loss, and a cholestatic liver enzyme profile. The patient was hospitalized and an evaluation was consistent with drug-induced acute hepatitis and cholestasis. The event was considered possibly related to study treatment and a contributory role could not be excluded. The subject also had a number of other potential contributory factors.

Further details on these clinical studies can be found in the ALN-TTRSC IB.

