## **5.6. Criteria for Dose Interruption, Dose Modification, or Discontinuation of Study Drug**

During the study, if a patient has an elevation of AST, ALT, or total bilirubin (unless due to Gilbert's Syndrome)  $>3 \times \text{ULN}$ , repeat assessments of AST, ALT, and total bilirubin should be performed within 72 hours. The patient should be followed closely, with LFT assessments performed weekly, and as medically indicated to guide patient management. Close monitoring may be discontinued when ALT, AST, and total bilirubin return to  $\leq 3 \times \text{ULN}$ . Additional, and repeat assessments, may be performed at the discretion of the Investigator.

- Dosing will be held for the following liver function test abnormalities: AST or ALT elevation of  $\geq 3 \times \text{ULN}$  in association with either total bilirubin elevation of  $\geq 1.5 \times \text{ULN}$  or gastrointestinal symptoms including nausea, vomiting and/or abdominal pain;
- AST or ALT elevation  $\geq 5 \times \text{ULN}$

Under these circumstances, the Medical Monitor and Investigator will decide on the appropriate action regarding frequency of repeat liver function tests and resumption of dosing.

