### **6.3. Estimated Glomerular Filtration Rate**

Estimated glomerular filtration rate will be calculated using the MDRD formula. If this parameter met eligibility criteria at Screening/Baseline, then dosing can proceed prior to receiving pre-dose Day 0 results.

The formula is as follows:

$$\text{GFR (mL/min/1.73 m}^2\text{)} = 175 \times (\text{S}_{\text{cr}})^{-1.154} \times (\text{Age})^{-0.203} \times (0.742 \text{ if female}) \\ \times (1.212 \text{ if African American}) \text{ (conventional units)}$$

This formula estimates GFR using 4 variables (serum creatinine, age, ethnicity, and gender). For precision, the serum creatinine values should be in mg/dL to 2 decimal places (eg, 0.95 mg/dL) OR values in  $\mu\text{mol/L}$  to the nearest whole number (e.g., 84  $\mu\text{mol/L}$ ). The following eGFR calculator can be used to determine eGFR: <http://nkdep.nih.gov/lab-evaluation/gfr-calculators.shtml>.

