#### **6.4.5. Clinical Laboratory Tests**

At the scheduled time points, samples for clinical laboratory tests will be collected before study drug dosing. The following clinical laboratory tests will be performed by each study site's local laboratory or a central laboratory:

---

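### Inclusion criterion 2 pairs units that disagree, about 1000-fold for bilirubin and about 100-fold for albumin

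*Protocol*

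**What the plan says.** Section 4.2, criterion 2, defines adequate liver function by AST and ALT relative to the upper limit of normal, followed by two absolute limits: "total bilirubin $< 2$ g/dL (34.2 $\mu$ mol/L), and albumin $> 3$ g/dL ( $> 4.35$ $\mu$ mol/L". The synopsis carries the same four figures, and no other section corrects them.

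Section 1.6.2 explains the purpose: "The risk of liver toxicity is lowered by requiring patients to have adequate liver function at study entry, as well as regular monitoring of LFTs".

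Section 6.4.5 lets safety laboratory tests be run by each site's "local laboratory or a central laboratory". It lists albumin and bilirubin without reporting units.

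On timing, Section 1.3 says "As of 05 January 2016, 25 patients have been treated with ALN TTRSC for approximately 8 months (range 1-13 months", and Section 4.1 says "Approximately 25 patients who completed participation in Study ALN-TTRSC-002 are expected to be enrolled in this extension study". The sentence in Section 1.3 does not name the study, but it follows the paragraph that introduces this extension.

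**The concern.** When a limit is printed in two units, a site may use whichever matches its laboratory report, so both must mean the same thing. Here they do not, and the two faults lie in opposite columns. A reader who uses g/dL throughout has a working albumin limit and no effective bilirubin limit. A reader who uses µmol/L throughout has a working bilirubin limit and no effective albumin limit. Neither column alone gives the complete criterion.

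The criterion puts numbers on an entry safeguard that Section 1.6.2 invokes right after reporting serious hepatic adverse events in the programme. Safety is the primary objective (Section 2.1), and hepatic events are of designated clinical interest (Section 7.1.1). If sites read the criterion differently, the treated population would not be the one the protocol describes, and eligibility deviations could not be judged against a single standard.

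**Working it through.** **Inputs from the protocol (Section 4.2 and synopsis).** Bilirubin: 2 g/dL, paired with 34.2 µmol/L. Albumin: 3 g/dL, paired with 4.35 µmol/L.

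**Assumed constants, not in the protocol.** Molar mass of bilirubin 584.66 g/mol (range tried 580 to 590); of albumin 65,000 to 69,000 g/mol, with 70,000 as an outer value; of creatinine 113.12 g/mol.

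**Formula.** Concentration in µmol/L = (10 × g/dL ÷ molar mass) × 1,000,000. The factor 10 converts g/dL to g/L.

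**Step 1: try to reproduce the printed bilirubin figure.**
- From 2 g/dL: 20 ÷ 584.66 × 1,000,000 = 34,208 µmol/L. Over 590 down to 580 g/mol the result is 33,898 to 34,483.
- Ratio to the printed figure: 34,208 ÷ 34.2 = 1000 (range 991 to 1008).
- From 2 mg/dL instead: 0.02 ÷ 584.66 × 1,000,000 = 34.2 µmol/L. The printed figure is reproduced only from the mg unit.

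**Step 2: try to reproduce the printed albumin figure.**

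| Assumed molar mass (g/mol) | 3 g/dL in µmol/L | Ratio to 4.35 | 4.35 µmol/L in g/dL |
|---|---|---|---|
| 65,000 | 462 | 106 | 0.028 |
| 66,500 | 451 | 104 | 0.029 |
| 69,000 | 435 | 100 | 0.030 |
| 70,000 | 429 | 99 | 0.030 |

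The printed 4.35 is not reproduced at any of these values. At 69,000 g/mol the result is 100 times 4.35.

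**Step 3: a check that starts from the printed pairs.** For a pair to be equivalent, the molar mass would have to be:
- bilirubin: 20 ÷ 0.0000342 = about 585,000 g/mol;
- albumin: 30 ÷ 0.00000435 = about 6.9 million g/mol.

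These are about 1000 and 100 times the assumed masses, so the choice of constant cannot explain the gaps.

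**Step 4: the effect of each printed figure.**

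| Limit | Read in g/dL | Read in µmol/L |
|---|---|---|
| Bilirubin | below 2000 mg/dL: no practical limit | below 34.2, about 2.0 mg/dL: operates |
| Albumin | above 3: operates | above about 0.03 g/dL: no practical limit |

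That the two void cells exclude no realistic patient rests on general physiology, not on a figure in the protocol.

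**Step 5: comparison within the protocol.** Section 6.3 gives creatinine examples of 0.95 mg/dL and 84 µmol/L. Converting, 0.0095 g/L ÷ 113.12 × 1,000,000 = 84.0 µmol/L. That pair agrees, so the mismatch is specific to criterion 2.

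**Step 6: is it an extraction fault?** The same four figures stand in the synopsis and in Section 4.2, which are formatted differently. A PDF reading error is unlikely.

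**The case against.** The arithmetic is hard to dispute; the case against concerns consequence.

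- **Likelihood.** A void figure takes effect only if a site applies bilirubin in g/dL or albumin in µmol/L. As a matter of general knowledge, laboratories seldom report in those units, and most investigators would recognise the slip. This carries weight and makes actual harm less likely. It does not remove the ambiguity: a site reporting bilirubin in mg/dL finds no limit printed in its own unit and must convert from one of two contradictory figures.
- **Mixed units across sites are inferred.** Section 6.4.5 says nothing about units, and acceptance of either unit in Section 6.3 concerns creatinine only. This stands. Mixed reporting is foreseeable, not demonstrated.
- **Other protection exists.** The AST/ALT limit in the same criterion is sound. Prior tolerance of the drug is required, the investigator may exclude unsuitable patients, and the on-study liver rules in Section 5.6 use multiples of the upper limit of normal. All true, but none supplies an entry limit for bilirubin or albumin.
- **Timing.** If Section 1.3 describes this study, enrolment was essentially complete by January 2016, and corrected text changes little prospectively. That moves the emphasis to which limits were applied to patients already enrolled.
- **Analysis.** The study is single-arm and descriptive, and the safety set includes everyone dosed, so no test or estimate is invalidated. Agreed; the defect lies in eligibility.

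**Conclusion.** The concern holds. In inclusion criterion 2 the paired units contradict each other by a factor of 1000 for bilirubin and 100 to 106 for albumin, in both places where the criterion appears. The size depends on assumed molar masses, but no plausible value closes either gap. This is an error in an eligibility threshold that the protocol itself treats as a hepatic safeguard, and it should be fixed. Its practical effect is probably limited, and nothing in the protocol shows that a patient was wrongly enrolled. The arithmetic shows which figures agree with each other; it does not establish which limits the sponsor intended.

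**What to change.** 1. The sponsor confirms the intended bilirubin and albumin limits and reconciles each unit pair in Section 4.2 and the synopsis. By unit arithmetic alone, 34.2 µmol/L corresponds to 2 mg/dL, and 3 g/dL to about 435 to 462 µmol/L (molar mass 69,000 down to 65,000 g/mol).
2. The sponsor confirms which values and units were used in eligibility checks, including for patients already enrolled, and records anyone who entered outside the confirmed limits.

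Cost: a short correction in two places through the amendment route in Section 9.2.3 (ethics committee or review board, and regulatory authority), plus one look at existing screening bilirubin and albumin for about 25 patients. No new procedure, visit or patient is needed.
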